6.3 Interim Analysis

Interim efficacy or safety analyses will be done to monitor TSH levels in all subjects. Subjects with persistently elevated TSH (5-10 mIU/mL) will be randomized for the

treatment phase. If TSH is >10 , a repeat test will be done within 1-2 weeks. If TSH remains >10 , the subject will not be randomized. Subjects that have TSH <5 may have a repeat TSH test within 1-2 weeks; this will be at the discretion of the study investigator. If TSH or repeat TSH (if applicable) is <5 , the subject will be considered to have normal levels of TSH and will not qualify to continue the study.

7 STUDY MEDICATION (INTERVENTION)

7.1 Description

Levothyroxine sodium tablets, USP contain synthetic crystalline L-3,3',5,5'-tetraiodothyronine sodium salt [levothyroxine (T₄) sodium]. Synthetic T₄ is identical to that produced in the human thyroid gland. 50 mcg levothyroxine tablets will be prescribed for anticipated doses ranging from 25 – 100 mcg/day (0.5-1 mcg/kg/day).

The placebo is generic lactase manufactured by Major Pharmaceuticals. Each caplet contains 3,000 FCC units of lactase enzyme (active ingredient). Inactive ingredients are: crospovidone, dicalcium phosphate, magnesium stearate, mannitol, microcrystalline cellulose, polyalditol, silicon dioxide, sodium citrate.

7.1.1 Packaging

A 3 month supply of tablets will be packaged in a child safe prescription container.

7.1.2 Labeling

Both levothyroxine and the generic lactase tablets are available commercially and will be labeled appropriately by the manufacturer. The investigational pharmacy will transfer a 3-month supply of tablets into a child-resistant vial and label with a patient-specific label that complies with all the federal, state and CFR requirements.

7.1.3 Dosing

Levothyroxine daily dose of 0.5 – 1 mcg/kg/day by mouth once per day.

7.1.4 Treatment Compliance and Adherence

Pill counts, monthly calendars for charting, and completion of a Supplement Adherence Questionnaire, a semi-structured interview, will be used to assess treatment compliance. Study staff will contact the families weekly to review adherence. The study psychologist will address with families issues that may be interfering with adherence.

7.1.5 Drug Accountability

Adequate records of study drug receipt and disposition will be maintained by the CHOP Investigational Pharmacy. The purpose of these records is to ensure regulatory authorities and the Sponsor that the investigational new drug will not be distributed to any person who is not a study subject under the terms and conditions set forth in this protocol. The study medication is to be prescribed by the Investigator or designee and may not be used for any purpose other than that described in this protocol. At study completion, all drug supplies including partially used and empty containers must be returned to the Study Coordinator.

8 SAFETY MANAGEMENT

8.1 Clinical Adverse Events

Clinical adverse events (AEs) will be monitored throughout the study. Following randomization, adverse events will be monitored using: (a) Home diary of adverse events (AE), rated by intensity (mild, moderate, severe). (b) Interview at each study visit to document intensity and frequency of AE.

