Study Treatment: A single blinded randomized trial of levothyroxine treatment (starting dose 0.5 – 1 mcg/kg daily) using a switching replication design. Subjects will be randomized into 2 groups of 10.

(Group 1) Delayed treatment group: 6 months of placebo followed by 6 months of levothyroxine treatment

(Group 2) Immediate treatment group: 12 months of levothyroxine treatment

Follow-Up: Studies will be obtained at baseline, 6 months, 12 months, and 18 months. Interim thyroid studies will be checked at 3 months, 6 weeks after randomization (month 7.5); month 13.5 and 6 weeks after any dose adjustment.

Efficacy Evaluations

TSH

T4

Anthropometry (HT-Z, WT-Z, BMI-Z),

body composition by DXA,

PWV & PWA

Blood lipid panel, non-HDL-C, lipoprotein subclass analysis, glucose, plasma insulin, HOMA-IR, hs-CRP, IL-6, PAI-1, adiponectin, leptin,

QOL, Body Image, physical activity assessment.

Safety Evaluations

To monitor for safety, data will be made available to investigators every 3 months. The PI will not be blinded to the treatment arm, will be making dose adjustments, and for safety purposes, TSH and T4 data will be available to the PI as soon as it is available.

Interview at 4 and 6 weeks after treatment initiation and at each visit to document intensity and frequency of any AE.

Any AEs and SAEs will be reported to the CTRC and the IRB within the allotted time frame.

Statistical And Analytic Plan

Standard mixed effects piecewise longitudinal data model ⁽²⁾ will be used to estimate in a single model both longitudinal (within subject) and cross-sectional (across subject) effects of the intervention. Cross-sectional comparisons will be possible for the second 6-month period of observation when ½ of subjects will be switched to treatment while the other ½ will take a placebo.

DATA AND SAFETY MONITORING PLAN

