Non-HDL-C	X		X			X		X
HbA1C	X		X			X		X
PAI-1	X		X			X		X
Hs-CRP	X		X			X		X
IL-6	X		X			X		X
Adiponectin	X		X			X		X
Leptin	X		X			X		X
Lipoprotein subclass analysis	X		X			X		X
T4	X	X	X		X	X	X	X
TSH	X	X	X		X	X	X	X
ANTITPO		X						
ANTITG		X						
Physical activity armband (Worn for 7 days after study visit)	X		X			X		X
Randomization				X				

Dispense study medication (placebo or levothyroxine)				X				
Dispense levothyroxine – both groups						X		
Dietary intake	XXX		XXX			XXX		XXX
Drug Compliance					X	X	X	X
Adverse Events					X	X	X	X

FIGURE 1: STUDY DIAGRAM

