3 INVESTIGATIONAL PLAN

3.1 General Schema of Study Design

This randomized, single-blinded, intervention study will take place at the CHOP outpatient CTSC and at Children's National Medical Center. Subjects with Down syndrome and subclinical hypothyroidism (TSH: 5-10 mIU/L) ages 8-20 years will be recruited for a trial of levothyroxine treatment, using a switching replication design. All subjects will be observed for 6 months. TSH and T4 will be obtained at the 3rd and 6th month of the observation period. If a subject has a TSH which has reverted to normal at 3 months, they will continue on to the 6-month check. Only subjects with persistently elevated TSH (5-10 mIU/mL) at 6 months will be enrolled in the randomized phase. While there is no standard definition of "persistently elevated," in this study, we consider TSH level that is 5-10 mIU/L at 0 and 6 months as "persistently elevated." If TSH is < 5 mIU/L at 0 months and the subject has a history of TSH 5-10 mIU/L, a repeat TSH may be drawn, at the discretion of the principle investigator, within 3-6 months; if TSH is < 5 mIU/mL at 6 months, a repeat TSH may be drawn, at the discretion of the investigator, within 1-2 weeks. If the repeat TSH is < 5 mIU/L, the subject will not be eligible to continue. If TSH is > 10 mIU/L during the first 6 months, a repeat TSH will be drawn within 1-2 weeks. If the repeat TSH is > 10 mIU/L, thyroid dysfunction will not be considered subclinical. The subject will be referred to an endocrinologist for definitive therapy. After 6 months of observation, subjects will be randomized to: Group 1 (6 months of placebo, followed by 6 months of levothyroxine) or Group 2 (12 months of levothyroxine). The initial levothyroxine dose will be 0.5 – 1 mcg/kg/day, with a goal of TSH desired range of 0.5 – 3 mIU/L. Subjects/families will be blinded to the treatment arm. Investigators will be unblinded to permit titration of levothyroxine dose. TSH and T4 will be measured after 6 weeks (month 7.5) of levothyroxine/placebo commencement (as a measure of efficacy of levothyroxine dose), and then at month 12. At month 12, levothyroxine will be initiated in Group 1 (delayed treatment), allowing for 6 months of treatment. Group 2 (immediate treatment) will continue an additional 6 months of levothyroxine (12 months total). TSH will be checked at 6 weeks (month 13.5) and at month 18 in both groups. Dose adjustments will be made at the discretion of the PI. TSH will be repeated 6 weeks after any dose adjustments, which may be in addition to the time points above if necessary. This switching replication design will permit using each child to serve as his/her own control and provides a placebo control period for each treated child. The goal is for 20 subjects to complete the 18 month study.

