8.3 Definition of an Adverse Event

An adverse event is any untoward medical occurrence in a subject who has received an intervention (drug, biologic, or other intervention). The occurrence does not necessarily have to have a causal relationship with the treatment. An AE can therefore be any unfavorable or unintended sign (including an abnormal laboratory finding, for example), symptom, or disease temporally associated with the use of a medicinal product, whether or not considered related to the medicinal product.

All AEs (including serious AEs) will be noted in the study records and on the case report form with a full description including the nature, date and time of onset, determination of non-serious versus serious, intensity (mild, moderate, severe), duration, causality, and outcome of the event.

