Children and adolescents with subclinical hypothyroidism are commonly treated with thyroid hormone replacement, even in the absence of data supporting treatment. Similarly, subclinical hypothyroidism is frequently treated in the setting of DS despite a dearth of evidence to support or negate intervention. The primary risk of thyroid hormone treatment in this 6 month observation followed by 6-12 month intervention study is excessive replacement leading to relative hyperthyroidism with TSH suppression; short-term symptoms include restlessness, irritability, tachycardia, palpitations, poor sleep, and weight loss. To minimize these risks:

- The family will be instructed to observe and report these symptoms/signs to the study team
 - TSH and T4 will be checked if signs/symptoms develop
-

-
- TSH and T4 will be checked 6 weeks after levothyroxine initiation, the time required to reach steady state; the dose will be titrated to maintain TSH in the normal range
 - If the initial TSH is within range, TFTs will be checked in another 14 weeks, sooner if symptoms arise
 - If a TSH is elevated or suppressed, the dose will be adjusted and TFTs repeated in 6 weeks to reassess thyroid status

The dose of levothyroxine replacement (0.5-1 mcg/kg/dy) is not expected to cause TSH suppression and symptoms of hyperthyroidism. A dose of 1 mcg/kg/day is used in the treatment of subclinical hypothyroidism in adults and is much lower than typical full replacement doses of 4-5 mcg/kg/day for age 6-12y; 2-3 mcg/kg/day for age >12 y but growth and puberty incomplete; and 1.7 mcg/kg/day for children in whom growth and puberty are complete. In fact, chronic suppressive doses of levothyroxine are routinely used following thyroidectomy and radioactive iodine ablation for thyroid cancer in adults and children. For children, this treatment means TSH is maintained in the low range (TSH < 0.1 mIU/L).(34); the major concern is the impact of years of suppressive therapy upon bone health. In this study, TSH will be measured and dose adjustments made for low TSH; thus, any subclinical hyperthyroidism induced by levothyroxine therapy will be brief. Morbidity from acute levothyroxine intoxication requires massive doses of levothyroxine (> 5-10 mg) and is not anticipated. The study team will remind families that, as with all medications, administration should be supervised by a parent and medications maintained out of reach of children.

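### Adverse events are elicited only after randomisation and without a new-or-worsened rule, so the subjective levothyroxine harms have no pre-dose record in Group 2 and only a placebo-period record in Group 1

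*Combined protocol and SAP*

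**What the plan says.** Section 8.1 opens broadly: "Clinical adverse events (AEs) will be monitored throughout the study". The only methods it then names are tied to allocation: "Following randomization, adverse events will be monitored using: (a) Home diary of adverse events (AE), rated by intensity (mild, moderate, severe"), and an interview at study visits. The synopsis, under Safety Evaluations, adds: "Interview at 4 and 6 weeks after treatment initiation and at each visit to document intensity and frequency of any AE". In Table 1 the row "Adverse Events" is marked at months 7.5, 12, 13.5 and 18 and is blank at months 0, 3 and 6.

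Section 8.3 limits an AE to someone who has received an intervention. It then takes in any unfavourable sign, "including an abnormal laboratory finding, for example), symptom, or disease temporally associated with the use of a medicinal product". Onset, intensity, duration and causality are recorded for each event. The section has no rule for conditions present before treatment.

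On the harms of over-replacement, section 9.4.2 says: "short-term symptoms include restlessness, irritability, tachycardia, palpitations, poor sleep, and weight loss". On the design, section 3.1 says: "This switching replication design will permit using each child to serve as his/her own control". Section 6.1.3 (Safety Analysis) covers who sees data and when; it plans no summary of AEs by arm or period.

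**The concern.** The introduction says that the risks of treating this population are unknown, and section 9.4.1 limits early stopping to safety and adverse events. AE data therefore carry more weight here than in most trials of this size.

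Restlessness and irritability can be present in a child before any tablet is taken. If nobody asks before the first dose, a long-standing symptom first mentioned at the four-week call looks the same as one that the drug caused. The own-control logic of the design is then lost for exactly those harms that only the child or family can report. Investigators know the allocation (section 9.1.2), so their causality ratings are made with that knowledge and without a pre-dose record to check against. The gap cannot be repaired at analysis, because the data will not exist.

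**Working it through.** The plan gives no AE rate, AE sample size or AE power, so there is no figure to reproduce. The power table in section 6.2 concerns continuous endpoints. The check is mainly of the text, with one illustration.

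**1. Which section 9.4.2 symptoms have a pre-dose value?** From Table 1 and section 5.1:
- Tachycardia: heart rate at months 0 and 6.
- Weight loss: weight at months 0 and 6.
- Poor sleep: armband worn after the visits at months 0 and 6.
- Restlessness, irritability, palpitations: no item specified. Medical history is taken at months 0 and 6, but nothing directs it to these symptoms. The PedsQL emotional scale is at best a partial proxy.

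So three of the six lack one. TSH and T4 are measured at months 0, 3 and 6.

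**2. Who has a same-instrument record before levothyroxine?** Group 1 has diary and interviews on placebo over months 6-12, then starts levothyroxine. Group 2 starts levothyroxine at month 6 and has none. In months 12-18 both groups take levothyroxine, so there is no concurrent control.

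**3. TSH.** Children are randomised with TSH 5-10 mIU/L at months 0 and 6. Those values precede any study product and fall outside section 8.3. Read literally, an unchanged value in that range at month 7.5 or 12 could be recorded as an AE. This is possible on placebo and also on levothyroxine, since section 6.1.1 expects some treated children to need dose adjustment after six weeks.

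**4. Effect on the randomised comparison (illustration).** Assumptions, none from the plan: 5% new onset on placebo over months 6-12 (c = 0.05), an added drug-caused risk of 30 points before overlap (e = 0.30), a background symptom persisting in a share b of both arms, and a two-sided Fisher test at 0.05. The plan supplies 10 per arm.
- True event probabilities: placebo c = 0.05; levothyroxine 1 − (1 − 0.05)(1 − 0.30) = 0.335. Difference 0.285.
- If background is counted, each probability p becomes b + (1 − b)p, so the difference is multiplied by (1 − b).
- b = 0.30: 0.335 v 0.5345, difference 0.1995.
- b = 0.50: 0.525 v 0.6675, difference 0.1425.
- Exact power: 13.6% at b = 0, 5.4% at b = 0.30, 3.2% at b = 0.50.

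If worsening of a background symptom counts as an event, and is detected as readily as a new onset, the b = 0 values return. If only new onsets count, power at b = 0.30 is 4.4%, which is no gain. The rule therefore has to say new **or worsened**.

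**5. What sample size alone does.** With no background at all, power is 4.1%, 13.6% and 48.3% for added risks of 20, 30 and 50 points. With 0 events in 10 children, the one-sided 95% upper bound is 1 − 0.05^(1/10) = 25.9%.

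**The case against.** The strongest reply is that months 6-12 are a randomised, family-blinded comparison with the same diary and interviews in both arms. Background common to both arms cannot reverse the difference. That stands, and it defeats the stronger reading that levothyroxine harms cannot be separated from background: they can, though less sharply. It does not cover months 12-18, or within-child attribution in Group 2.

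Second, Group 1 does have a within-child baseline, on placebo with the same tools. This also stands, and is why the gap lies mainly in Group 2.

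Third, onset dates and causality are recorded, and symptoms are reviewed at four and six weeks. This helps, but the onset of a long-standing symptom would rest on recall.

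Fourth, the blanks in Table 1 agree with section 8.3, which defines AEs only after an intervention. That is fair: the blanks are not an error in themselves. But the opening sentence of section 8.1 then promises more than any stated method delivers. The synopsis wording about each visit could be read to include months 0 and 6, but section 8.1 and Table 1 do not support that.

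Finally, 10 per arm limits harm detection at least as much as the missing rule does. The working confirms this. It is a reason not to waste an available baseline, and also a reason not to overstate what the baseline would bring.

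**Conclusion.** The point holds as a cheap improvement to harm attribution, not as a threat to the trial's validity. Elicitation starts after randomisation, no new-or-worsened rule exists, and three of the six symptoms in section 9.4.2 have no pre-dose record on the AE instruments. For background shared by both arms, the consequence over months 6-12 is dilution by a factor (1 − b). The size depends on background and drug-effect rates that the plan does not give, so the figures above are illustrations only.

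A persisting TSH is a separate matter. Levothyroxine is titrated to lower it, so under a literal reading it need not be counted equally in the two arms. I put no number on this, because the plan neither adopts nor excludes that reading.

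A reader might also infer two things that the documents do not support:
- That the entry TSH itself is an AE. The month 0 and 6 values precede any product.
- That counts run three to one against levothyroxine, from 10 × 12 + 10 × 6 = 180 child-months against 10 × 6 = 60 on placebo. That ratio is exposure time, would remain after any change to AE collection, and vanishes with rates or a months 6-12 comparison; no pooled raw count is planned. Nor can the pill-free observation months be pooled with placebo to gain precision.

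**What to change.** 1. In section 8.1 and Table 1, record the section 9.4.2 symptom list, with frequency and intensity, at Study Visit #2 before the first dose, and ideally at Study Visit #1 as well. Randomisation follows Study Visit #2, so this record is made before anyone knows the allocation. Use the same list in both arms at the AE interviews already planned.
2. In section 8.3, define an on-treatment AE as new or worsened relative to that record. An unchanged entry-range TSH is then not an AE, while newly abnormal values, including TSH suppression, still count. TSH and T4 should not be taken out of AE reporting altogether: suppression is part of the primary risk named in section 9.4.2, and removing it would hide it.
3. In section 6.1.3, tabulate AEs by arm and period (months 6-12 and 12-18) with exposure time, and show pre-dose data separately from placebo.
4. Reconcile the opening sentence of section 8.1 with Table 1 and section 8.3.

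The cost is a few minutes of added family burden at an existing visit, a short form and some protocol wording. No extra visit is needed.

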8.2 Adverse Event Reporting

The Investigator is responsible for recording and reporting unanticipated problems related to research that occur during and after study treatment. All on-site SAEs will be reported to the IRB in accordance with IRB policies. AEs that are not serious will be summarized in narrative or other format and submitted to the IRB at the time of continuing review.

8.3 Definition of an Adverse Event

An adverse event is any untoward medical occurrence in a subject who has received an intervention (drug, biologic, or other intervention). The occurrence does not necessarily have to have a causal relationship with the treatment. An AE can therefore be any unfavorable or unintended sign (including an abnormal laboratory finding, for example), symptom, or disease temporally associated with the use of a medicinal product, whether or not considered related to the medicinal product.

All AEs (including serious AEs) will be noted in the study records and on the case report form with a full description including the nature, date and time of onset, determination of non-serious versus serious, intensity (mild, moderate, severe), duration, causality, and outcome of the event.

8.4 Definition of a Serious Adverse Event (SAE)

An SAE is any adverse drug experience occurring at any dose that results in any of the following outcomes:

- death,
- a life-threatening event (at risk of death at the time of the event),
- requires inpatient hospitalization or prolongation of existing hospitalization,
- a persistent or significant disability/incapacity, or
- a congenital anomaly/birth defect in the offspring of a subject.

Important medical events that may not result in death, be life-threatening, or require hospitalization may be considered a serious adverse drug event when, based upon appropriate medical judgment, they may jeopardize the subject and may require medical or surgical intervention to prevent one of the outcomes listed in this definition.

A distinction should be drawn between serious and severe AEs. A severe AE is a major event of its type. A severe AE does not necessarily need to be considered serious. For example, nausea which persists for several hours may be considered severe nausea, but would not be an SAE. On the other hand, a stroke that results in only a limited degree of disability may be considered a mild stroke, but would be an SAE.

8.4.1 Relationship of SAE to study drug or other intervention

The relationship of each SAE to the study intervention should be characterized using one of the following terms in accordance with CHOP IRB Guidelines: definitely, probably, possibly, unlikely or unrelated.

8.5 IRB/IEC Notification of SAEs and Other Unanticipated Problems

The Investigator will promptly notify the IRB of all on-site unanticipated, serious Adverse Events that are related to the research activity. Other unanticipated problems related to the research involving risk to subjects or others will also be reported promptly. Written reports will be filed using the eIRB system and in accordance with the timeline below. External SAEs that are both unexpected and related to the study intervention will be reported promptly after the investigator receives the report.

Type of Unanticipated Problem	Initial Notification (Phone, Email, Fax)	Written Report
Internal (on-site) SAEs Death or Life Threatening	24 hours	Within 2 calendar days
Internal (on-site) SAEs All other SAEs	7 days	Within 7 business days
Unanticipated Problems Related to Research	7 days	Within 7 business days
All other AEs	N/A	Brief Summary of important AEs may be reported at time of continuing review

